6. DATA SETS ANALYZED (STUDY POPULATIONS)

6.1. Safety Set

The safety set will consist of all patients who received at least 1 dose of ALXN1210; this population will be used for the safety analyses.

6.2. Full Analysis (FA)

The full analysis set (FA) will consist of all patients in the safety set with a baseline and at least 1 LDH measurement post-first ALXN1210 dose. The FAS will be used for all efficacy analyses.

6.3. Other Sets

The PK analysis set will consist of all patients who have sufficient serum concentration data to enable the calculation of PK parameters. The PK analysis set will be used for PK summaries.

The PD analysis set will consist of all patients with a baseline and at least 1 PD measurement post-first ALXN1210 dose. The PD analysis set will be used for all PD summaries.

The immunogenicity analysis set will consist of all patients who have an ADA sample both pre and post first ALXN1210 dose. The immunogenicity analysis set will be used for immunogenicity summaries.

7. STATISTICAL ANALYSIS

All data collected in this study will be documented using summary tables, figures, and data listings. For categorical variables, frequencies and percentages will be presented for each cohort, and for the combined cohorts. For continuous variables, descriptive statistics (n, mean, median, SD, minimum, maximum) will be presented for each cohort, and for the combined cohorts.

Descriptive statistics for PK parameters will include the number of observations, mean, SD, coefficient of variance (CV), median, minimum, maximum, geometric mean, and geometric %CV.

7.1. Study Patients

7.1.1. Disposition of Patients

A summary of patient disposition for all treated patients will be presented and will include a summary of the number and percentage of screened patients, screen failures, and treated patients. The number and percentage of patients who completed the study through the end of the maintenance period or discontinued/withdrew from the study through the end of the maintenance period, along with reason for discontinuation/withdrawal will be presented.

The number and percentage of patients in each analysis set will be tabulated.

By-patient data listings with disposition will be provided as well as a listing of patients who did not meet the inclusion/met the exclusion criteria.

7.1.2. Protocol Deviations

All protocol deviations will be listed for all patients in the safety set.

7.1.3. Demographics, Disease Characteristics, and History

All demographic and baseline characteristics information will be summarized using the FA Set. Summary statistics will be presented by cohort and overall. By-patient listings of demographic information, disease characteristics, PNH medical history and medical/surgical history will be produced.

7.1.3.1. Demographics

The following demographic variables will be summarized:

- Sex
- Race
- Ethnicity
- Age (years) at First Infusion
- Baseline Weight
- Baseline Height

- Baseline Body Mass Index (BMI)
- Subjects of Japanese Descent

7.1.3.2. Disease Characteristics and PNH Medical History

The following PNH disease characteristics will be summarized.

- Age (years) at PNH diagnosis.
- Method of PNH diagnosis.
- Years from PNH diagnosis to informed consent.
- PNH clone size (granulocyte, and red blood cell (RBC)) at screening.
- Peripheral red blood cell (pRBC) transfusion requirements in the year prior to receiving ALXN1210 including number of transfusion episodes and units transfused.
- First PNH symptoms.
- History of any major adverse vascular event (MAVE). The number of patients (n, %) with any history of MAVE and within a particular MAVE category (e.g. thrombophlebitis/deep vein thrombosis, pulmonary embolus, myocardial infraction, etc.) will be displayed.

7.1.3.3. Medical / Surgical History and Baseline Physical Examination

Medical history information will be summarized by cohort for the safety and FA set (if different) using the number (%) of patients who have a medical or surgical history. Likewise, baseline physical examination information will be summarized by cohort.

7.1.4. Prior and Concomitant Medications / Therapies

Prior and concomitant medications will be summarized using the Safety set. Prior medications are defined as medications taken prior to the first study infusion and include all medications taken within 28 days prior to informed consent as well as all Neisseria meningitidis vaccinations administered within 3 years of dosing with ALXN1210. Concomitant medications are defined as medications received by the patients on/after first study infusion.

Medications will be coded using the World Health Organization Drug Dictionary version in use by Alexion at the time of the analysis. Medication summaries i.e. number (%) of patients using prior and concomitant medications will be presented by WHO-DRUG Anatomical Therapeutic Chemical (ATC) and by WHO-DRUG generic name.

Listings of prior and concomitant medications will be produced.

7.2. Efficacy Analyses

Efficacy analyses will be performed on the Full Analysis Set (FAS).

7.2.1. Primary Analysis

The primary efficacy endpoint is the change from baseline in lactate dehydrogenase (LDH) levels to Day 253. Absolute LDH levels, and the change and percent change from baseline will be summarized at all study visits, by cohort and overall. Baseline is defined as the average of all available assessments prior to first ALXN1210 infusion.

A mixed model for repeated measures (MMRM) (Mallinckrodt, 2001; Mallinckrodt, 2004) with the fixed, categorical effect of visit and fixed, continuous effect of baseline LDH levels as covariates will be fit to test whether changes and percent changes differ from zero at each time point for the combined cohorts. An unstructured covariance matrix will be used to model the within-patient errors. If this analysis fails to converge, the following structures will be tested, and the final covariance structure will be determined by Akaike's information criterion: first order autoregressive, compound symmetry, and Toeplitz method. The Kenward-Roger approximation will be used to estimate denominator degrees of freedom. Confidence intervals (CI) and p-values from the model will be presented.

As a sensitivity analysis, changes and percent changes from baseline will be analyzed using the Wilcoxon signed-rank test. Last observation carried forward (LOCF) will be used for patients with missing Day 253. If MMRM analysis fails to converge given the small sample size in this study, Wilcoxon signed-rank test will be used for the primary analysis of LDH.

The number (%) of patients achieving LDH levels at or below 1.0 times upper limit of normal (1.0 x ULN) and levels at or below 1.5 x ULN) will be displayed.

Mean (\pm 95% CI) of absolute LDH levels, and the change and percent change from baseline will be plotted over time, by cohort and overall.

By-patient data listings of LDH data will be produced.

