**Statistical Methods:**

All data collected in this study will be documented using summary tables, figures, and data listings. For categorical variables, frequencies and percentages will be presented for each cohort and for the combined cohorts. For continuous variables, descriptive statistics (n, mean, median, standard deviation [SD], minimum, maximum) will be presented for each cohort and for the combined cohorts. Safety analyses will be performed on the Safety Set, which includes all patients who receive at least 1 dose of ALXN1210. Efficacy analyses will be performed on the Full Analysis Set, which includes the Safety Set subset with a baseline and at least 1 postbaseline LDH measurement.

Immunogenicity: Immunogenicity, as measured by ADA, will be summarized in tabular form by treatment.

Efficacy: The absolute LDH level, and the change and percent change from baseline will be summarized at all study visits. Baseline is defined as the average of all available assessments on or prior to first infusion with ALXN1210. A mixed model for repeated measures, with the fixed, categorical effect of visit and fixed, continuous effect of baseline LDH levels as covariates will be fit to test whether the changes and percent changes differ from zero at each time point. An unstructured covariance analysis will be used to model the within-patient errors. If this analysis fails to converge, the following structures will be tested and the final covariance structure will be determined by Akaike's information criterion: first-order autoregressive, compound symmetry, and Toeplitz method. The Kenward-Roger approximation will be used to estimate denominator degrees of freedom. The secondary endpoints will be similarly analyzed, as appropriate.

Change from baseline in the quality of life instrument scores, FACIT-Fatigue scale and the EORTC scale, will be summarized descriptively at all visits.

Transfusion rates and the incidence rate of MAVEs will be summarized.

**Pharmacokinetics:** Mean serum ALXN1210 concentrations versus nominal time and individual serum ALXN1210 concentrations versus actual time will be graphically presented. Descriptive statistics (mean, SD, coefficient of variance [CV], median, minimum, maximum, geometric mean, and geometric percent [CV]) of the serum concentrations will be provided, as appropriate.

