-  Female patients of childbearing potential only. Serum pregnancy test at screening only; urine pregnancy test at all other time points. A negative urine test result is required prior to administering ALXN1210 to female patients on dosing days.
-  Investigator assessment of the following events: fatigue, abdominal pain, dyspnea, dysphagia, chest pain, and erectile dysfunction. Symptoms of disease burden will be captured through the QoL questionnaires.
-  Abbreviated physical examination consists of a body system relevant examination based upon Investigator judgment and subject symptoms.
-  Obtain triplicate 12-lead ECGs at screening and prior to the first dose on Day 1, and single 12-lead ECGs on Day 253.
-  Clinical safety laboratory measurements will be collected predose on dosing days. Follicle-stimulating hormones and estradiol levels will be measured at least twice during screening, only in order to confirm postmenopausal status.
-  At least two samples must be collected at least one day apart during the screening period for LDH testing.
-  Assessment for safety, as well as the following parameters as secondary endpoints: free hemoglobin, haptoglobin, reticulocyte count, and D-dimer.
-  Obtain predose on Days 1, 29, 85, 141, 197, and 253.
-  Please refer to [Table 17](#) for cohort-specific sampling time points.
-  To include serum for exploratory PD assays; please refer to [Table 17](#) for cohort-specific sampling time points.
-  Immunogenicity samples will be collected predose on dosing days. Please refer to [Table 18](#) for cohort-specific sampling time points.
-  Functional Assessment of Chronic Illness Therapy-Fatigue Scale, version 4.0 and European Organisation for Research and Treatment of Cancer, Quality of Life Questionnaire-Core 30 Scale, Version 3.0.
-  An induration or reaction of <10 mm will not be listed as an adverse event unless it persists for more than 24 hours, at which time the patient must inform the study staff immediately and proceed to the nearest hospital emergency department.
-  Patient should assess infusion site pain using a 100 mm VAS. The VAS should be completed as soon as practical after completion of the infusion.

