7.2.1.4. Hypothesis Testing and Significance Level

Hypothesis testing for the change and percent change in LDH from baseline to Day 253 will be two-sided and performed at the 0.05 level of significance. For all the other parameters, p-values will be provided descriptively. Estimates of treatment effect on efficacy parameters will be accompanied by two-sided 95% confidence intervals, as indicated for the specific analysis.

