9.3. Sample Size, Power, and Randomization

A sample size of 20 patients from the combined cohorts provides approximately 95% power to detect a mean paired difference in LDH from baseline of -40% at Day 253, with an estimated SD of 45%. This was based on a 2-sided, paired t-test, with a 5% type 1 error rate. To account for a possible 15% dropout rate and additional patients in screening, up to 26 patients will be enrolled.

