9.4. Technical Specifications for Derived Variables

The following derived data will be calculated prior to analysis.

Age

Age will be presented as the number of years between date of birth and the reference date. The following ages (in years) may be computed using the formula (reference date – date of birth)+1/365.25, with reference dates indicated as follows:

Table 3: Age and reference date

AGE	REFERENCE DATE
• Age at Enrollment	• Date of Signing ICF
• Age at PNH Diagnosis	• Date of PNH diagnosis
• Age at First Infusion	• Date of First Infusion

For all dates in Table 3, in cases where only the month and year are provided for a date, the day for the date will be imputed as 15. Missing month will be imputed as June. In cases where the day is observed but the month is missing, the date will be imputed as June 15.

Disease Duration

PNH disease duration will be presented as the number of years between the date of first infusion and the date of PNH diagnosis (i.e. $\text{INT}[(\text{Date of first infusion} - \text{Date of PNH diagnosis} + 1)/365.25]$ or a similar formula using months and years or years only in the event of partial dates for PNH diagnosis).

Definition of Baseline Values

Baseline is defined as the last non-missing assessment value prior to the first ALXN1210 dose unless otherwise specified.

Baseline for LDH

Baseline for LDH is defined as the average of all available assessments prior to first ALXN1210 infusion.

Baseline for Electrocardiograms (ECGs)

The mean of the three pre-dose readings on Day 1 for heart rate and RR, PR, QT, and QTcF will be considered the baseline values for each patient. If values are not available for all three readings, an average will be calculated based on the available non-missing values.

Change from Baseline

Change in values from baseline will be calculated as follows.

Change in Value = (subsequent value – baseline value), given that both the baseline value and subsequent value are non-missing.

Percent Change in Assessments from Baseline

Percent change in values from baseline will be calculated as follows.

$$\% \text{ Change in Value} = \frac{\text{Change in Value}}{\text{Baseline value}} \times 100$$

where Change in Value = (subsequent value – baseline value), given that the baseline value is non-missing and non-zero and the subsequent value is non-missing.

ECG Respiratory Rate

For records with missing RR, HR (beats/min) will be used to calculate RR (Milliseconds) as follows:

$$RR = 60000 / HR$$

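### The model-based Day 253 confidence interval for LDH change is conditional on the observed baselines; for the population mean change it is too narrow, by an amount the documents do not fix

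*SAP*

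**What the plan says.** SAP 7.2.1 fits one MMRM to the combined cohorts. Visit is categorical, and the "fixed, continuous effect of baseline LDH levels as covariates will be fit to test whether changes and percent changes differ from zero", with a test for every visit. Covariance is unstructured, with simpler structures as fallbacks and Kenward-Roger degrees of freedom. Then: "Confidence intervals (CI) and p-values from the model will be presented". Protocol 16.6 and the synopsis specify the same model (synopsis: "fixed, continuous effect of baseline LDH levels as covariates will be fit to test whether the changes and percent changes differ from zero").

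Baseline is a measured quantity. SAP 9.4: "Baseline for LDH is defined as the average of all available assessments prior to first ALXN1210 infusion". The footnotes to protocol Table 4 give the likely number of values: "At least two samples must be collected at least one day apart during the screening period for LDH testing", and "Clinical safety laboratory measurements will be collected predose on dosing days". With the Day 1 sample, that makes about three.

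Under SAP 7.2.1.4 the LDH test "will be two-sided and performed at the 0.05 level of significance". SAP 9.3 sizes the study for a mean change of −40% with SD 45% in 20 patients: "This was based on a 2-sided, paired t-test, with a 5% type 1 error rate".

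Neither document gives the baseline value at which the Day 253 mean is evaluated, or says whether inference is conditional on the baselines observed.

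**The concern.** In a two-arm trial, sampling variation in baseline largely cancels from the treatment difference. Here there is no comparator, and the estimate is a single mean change. If another sample of patients had been enrolled, their mean baseline would differ, and with it their mean change. A paired t interval carries that variation. The model interval removes it with the baseline slope and never puts it back.

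At stake is the stated precision of the primary endpoint. The study is planned on one variance and reported on a smaller one, and nothing tells the reader that the two intervals describe different quantities. Absolute change, which is the endpoint as worded, is the more exposed scale: it contains minus baseline, so it tends to have a negative slope on baseline.

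**Working it through.** **1. The plan's own figure.** Inputs from SAP 9.3: n = 20, mean −40, SD 45, two-sided 5% paired t.
- Noncentrality = (40/45) × √20 = 3.975 on 19 df, giving power of 96.5%. This agrees with the stated figure of about 95%.
- Unadjusted 95% half-width = 2.093 × 45/√20 = 21.1 percentage points.

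**2. The missing term.** Assume complete data and a visit mean taken at the sample mean baseline. The Day 253 estimate is then the raw mean change.
- Model variance = Var(residual)/n.
- Variance for the population mean change = [Var(residual) + slope² × Var(baseline)]/n.
- SE ratio = √(1 − R²), with R the correlation of baseline and change. It is 0.95 at R² = 0.10, 0.87 at 0.25 and 0.71 at 0.50.

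This is exact for one visit and approximate for an MMRM with a common slope. Kenward-Roger takes the design matrix, including baseline, as given and does not add the term. The fallback covariance structures share the gap; the Wilcoxon test does not.

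**3. Size if percent change is independent of baseline, at the planning values.** The slope of absolute change on baseline is −0.40. In units of the squared mean baseline, the omitted part is 0.16 × CV² and the residual part is 0.45² × (1 + CV²).
- CV 20%: R² = 0.0064/(0.0064 + 0.2106) = 0.03, ratio 0.98.
- CV 40%: R² = 0.0256/(0.0256 + 0.2349) = 0.10, ratio 0.95.
- CV 60%: R² = 0.0576/(0.0576 + 0.2754) = 0.17, ratio 0.91.

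Simulated single-visit coverage for absolute change was 94.4, 92.5 and 89.8%. A five-visit unstructured MMRM gave 94.4, 92.4 and 91.4%. Percent change stayed at about 95%.

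**4. Other assumed settings near SD 45%.** These use lognormal LDH, a 40% fall in the mean level, a baseline averaging three pre-dose values (log-scale correlation 0.7), n = 20 and a single visit.

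| Baseline CV | Day 253 CV | Pre/post correlation | Implied SD of percent change | Coverage, absolute change |
|---|---|---|---|---|
| 40% | 60% | 0 | 49 | 83% |
| 40% | 80% | 0.3 | 47 | 89% |
| 60% | 60% | 0.3 | 47 | 78% |

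Steps 3 and 4 together give roughly 78 to 94% for absolute change. For percent change they give about 89 to 95%, against about 92 to 95% for the paired t, so much of that shortfall is skewness. Adding the missing term brought absolute-change coverage back to about 94 to 96%.

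**5. What lower coverage would need.** Suppose Day 253 LDH is unrelated to baseline, with mean 1.2 and SD 0.4 × ULN, and mean baseline is 6 × ULN with CV 20%. Then slope ≈ −1 and R² = 1.2²/(1.2² + 0.4²) = 0.90, for a ratio of 0.32. Simulated five-visit MMRM coverage for absolute change was 47%, falling to 18% at baseline CV 60%.

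**6. Type I error.** Take no mean change, equal variances and three exchangeable pre-dose values with correlation ρ. For ρ = 0.3: Var(B) = (1 + 0.6)/3 = 0.533; Cov(B, change) = 0.3 − 0.533 = −0.233; Var(change) = 1 + 0.533 − 0.6 = 0.933. So R² = 0.233²/(0.533 × 0.933) = 0.109, and the true size is P(|t₁₈| > 2.101 × √0.891) = 6.3%. At ρ = 0.5, 0.7 and 0.9 it is 5.7, 5.3 and 5.1%. If half the within-patient variance is slow drift, the sizes for ρ = 0.9, 0.7, 0.5 and 0.3 are 5.3, 6.0, 7.0 and 8.4%. With a single-value baseline, ρ = 0.3 would give 10.8%; averaging is what keeps the inflation small.

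**The case against.** Inference conditional on observed covariates is the ordinary reading of a fixed-effect covariate, and on that reading the interval is correct. No section names the population mean change as the target; that follows only from the paired t-test used for sizing. This stands: the gap is an unstated estimand, not a wrong model.

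The SAP also plans other results: overall means and SDs of change, from which an unadjusted interval follows directly; plots with 95% intervals; and a Wilcoxon sensitivity analysis. These help a careful reader. But the SAP does not say whether the plotted intervals are raw or model-based, and none of these corrects the model interval reported for the primary endpoint.

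A reader might infer that coverage must be far below 95%. Setting the CV at 40% both at baseline and at Day 253, for instance, gives 74 to 81% for absolute change as the pre/post correlation runs from 0 to 0.7. That setting implies a percent-change SD of only 15 to 37 points, below the 45 in SAP 9.3, and too little post-treatment spread inflates R². The 18 to 47% figures need tighter clustering still. The documents support neither as the expected case.

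Finally, dropout (allowed for at 15%) was not simulated, and the algebra assumes complete data.

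**Conclusion.** The point holds as a matter of precision. Read as an interval for the population mean change, the Day 253 model interval is too narrow whenever baseline and change are correlated. Near the planned SD the loss for absolute change runs from slight to material; for percent change it is small beyond what skewness already costs the paired t. The ranges rest on assumed baseline spread, correlation and distribution, n = 20, one visit, complete data and evaluation at the mean baseline. Confidence is high on direction and low on magnitude.

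A reader might go further and infer that the primary test is invalid or that the LDH conclusion is at risk. The documents do not support that. With the averaged baseline the type I inflation is small, planned power is 96.5%, and at the planning values even the unadjusted interval (−40 ± 21.1, or −61.1 to −18.9) excludes zero.

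**What to change.** In SAP 7.2.1, state that the estimand is the population mean change at Day 253 and that the visit mean is evaluated at the sample mean baseline. Then either add slope² × s_B²/n to its variance, where s_B² is the sample variance of baseline, or drop the baseline covariate. Adding the term was slightly conservative under the null in simulation (size 3.3 to 4.4%).

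If conditional inference is intended, the minimum is to label the model interval as conditional on the observed baselines, name the reference baseline, and report the unadjusted overall Day 253 interval beside it.

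Record the change in SAP 4.1, which now lists only the Cohort 4 Day 281 addition. The cost is a few lines of text, a wider reported interval and a documented departure from protocol 16.6; no new data are needed. Carrying the change over to the haematology and FACIT-Fatigue models is optional. Their baseline is a single last value, so averaging gives no relief there, but SAP 7.2.1.4 makes their p-values descriptive.

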Cohort	Patients	Induction	Maintenance
1	6	1400 mg on Day 1 1000 mg on Day 15	1000 mg on Day 29 and then every 28 days or 4 weeks (Days 57, 85, 113, 141, 169, 197, 225) 8 maintenance doses
2	6	2000 mg on Day 1 1600 mg on Day 22	1600 mg on Day 43 and then every 42 days or 6 weeks (Days 85, 127, 169, 211) 5 maintenance doses
3	6	1600 mg on Day 1 1600 mg on Day 15	2400 mg on Day 29 and then every 56 days or 8 weeks (Days 85, 141, 197) 4 maintenance doses
4	6 to 8	3000 mg on Day 1	5400 mg on Day 29 and then every 84 days or 12 weeks (Days 113 and 197) 3 maintenance doses

Figure 1: ALXN1210-PNH-201 Study Schematic

The study objectives are as follows:

Primary Objective

The primary objective of this study is to evaluate the efficacy, safety, and tolerability of multiple doses of ALXN1210 administered IV to complement inhibitor treatment-naïve patients with PNH.

Secondary Objectives

The secondary objectives are to:

- Characterize the PK and PD effects of multiple doses of ALXN1210 administered IV to complement inhibitor treatment-naïve patients with PNH.
- Investigate the immunogenicity of ALXN1210 administered IV to complement inhibitor treatment-naïve patients with PNH.

Additional information about the study can be found in the protocol.

A clinical study report (CSR) will be produced after the end of the maintenance period plus the Day 281 visit for cohort 4, and will include safety, efficacy, Pharmacokinetics (PK) and Pharmacodynamics (PD) analyses. The Day 281 visit (the first dose in the Extension Period) will be included for Cohort 4 as patients in Cohort 4 receive their last dose during Maintenance on Day 197 and Day 281 would provide safety and efficacy at the trough concentration of ALXN1210. This statistical analysis plan (SAP) outlines only the analyses that are to be included in that report.

A final CSR will be produced at study completion and will include data on all patients in the study at the end of the extension period.

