4.1. Changes from Analyses Specified in the Protocol

There are no changes from analyses specified in the protocol apart from the inclusion of data up to the Day 281 visit for Cohort 4 (the first dose in the Extension Period) in the analyses.

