7.2.2. Secondary Analyses

Descriptive statistics for the secondary endpoints of absolute, changes and percentage changes from baseline in hemolysis-related hematologic parameters (free hemoglobin, haptoglobin, reticulocyte count, PNH red blood cell (RBC) clone, and D-dimer) will be produced for each visit, by cohort and overall. Baseline is defined as the last non-missing assessment value prior to the first ALXN1210 infusion. For any hemolysis-related hematologic parameter with a result value below or above the limit of quantification (i.e., a result of $<x$ or $>x$) the numeric result without the $<$ or $>$ symbol will be used in the analyses. The changes and percentage changes from baseline in hemolysis-related hematologic parameters will be analyzed in the same manner as described for the primary efficacy endpoint utilizing the MMRM approach.

As a sensitivity analysis, changes and percent changes from baseline will be analyzed using the Wilcoxon signed-rank test. Last observation carried forward (LOCF) will be used for patients with missing Day 253.

Individual patient plots of the hemolysis-related parameters will be produced. The following figures will also be produced by cohort and overall:

- Mean ($\pm 95\%$ CI) endpoint values over time
- Mean change/percentage change ($\pm 95\%$ CI) from baseline in endpoint values over time

Shift tables will be produced for all study visits by cohort and overall for the following clinical manifestations of PNH: fatigue, abdominal pain, dyspnea, dysphagia, chest pain, and erectile dysfunction.

By-patient data listings containing all secondary endpoints will be produced.

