The scoring guideline for the FACIT-FATIGUE and EORTC QLQ-C30 instruments will be used to calculate a FACIT-FATIGUE score and the different EORTC QLQ-C30 scale scores. Refer to Section 9.5 for a more detailed description of the FACIT-FATIGUE score and EORTC QLQ-C30 and the scoring methods. Descriptive statistics of FACIT-FATIGUE scores and changes from baseline in FACIT-FATIGUE scores will be produced for all study visits at which they are collected, by cohort and overall. Changes from baseline will be analyzed in the same manner as described for the primary efficacy endpoint utilizing the MMRM approach and Wilcoxon signed-rank test.

The number of any treatment emergent MAVEs (n) and number of patients with events (n, %) will be displayed by cohort and overall. Each of the MAVE categories will be similarly summarized. Patients having multiple MAVEs within a category will be counted once in that category.

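### Does the pooled LDH model need a stated rule for Cohort 4's Day 281 visit, and the report a separate trough-matched summary?

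*SAP*

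**What the plan says.** SAP 7.2.1 states: "The primary efficacy endpoint is the change from baseline in lactate dehydrogenase (LDH) levels to Day 253". The model has visit as a category and baseline LDH as a covariate, has no cohort term, and "will be fit to test whether changes and percent changes differ from zero at each time point for the combined cohorts". The covariance starts unstructured. "If this analysis fails to converge, the following structures will be tested": first-order autoregressive, compound symmetry and Toeplitz, chosen by Akaike's criterion. The Wilcoxon signed-rank test is the last resort. SAP 7.2.1.4 limits formal testing: "Hypothesis testing for the change and percent change in LDH from baseline to Day 253 will be two-sided", at the 0.05 level, with all other p-values descriptive.

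The same model carries over to two other places. In SAP 7.2.2, "hemolysis-related hematologic parameters will be analyzed in the same manner as described for the primary efficacy endpoint utilizing the MMRM approach". For FACIT-Fatigue in SAP 7.2.3, "Changes from baseline will be analyzed in the same manner as described for the primary efficacy endpoint utilizing the MMRM approach".

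SAP 4.1 reports that the protocol's analyses stand unchanged, "apart from the inclusion of data up to the Day 281 visit for Cohort 4 (the first dose in the Extension Period) in the analyses". SAP 4 gives the reason: "Day 281 would provide safety and efficacy at the trough concentration of ALXN1210". SAP 7.2.3 (transfusions), 7.3 (safety listings) and 7.3.1 (exposure) each name Day 281 as Cohort 4's cut-off in place of Day 253. SAP 7.2.1 and 7.2.2 do not mention it.

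**The concern.** Two things look wrong at first.

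- **Model.** If Cohort 4's extra data are in the analyses and the model tests every time point, a programmer could add Day 281 as a visit level. Cohort 1 also has a Day 281 visit (Protocol Table 8), but this report takes in only Cohort 4's, so the level would rest on 6 to 8 patients. The unstructured fit would break down, and the primary analysis would move to a simpler covariance because of an unstated visit list.
- **Comparison.** Day 253 summaries set Cohort 4 in mid-interval beside three cohorts at trough. In a regimen-ranging study meant to inform Phase 3, that could flatter the longest interval. SAP 4 adds Day 281 to show efficacy at trough, yet no LDH or hemolysis-marker table pairs that value with the Day 253 values of the other cohorts.

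**Working it through.** **1. The plan's own figure.** SAP 9.3 gives n = 20, mean change -40%, SD 45%, two-sided paired t-test at 5%. The noncentrality is (40/45) × √20 = 3.98 on 19 df. Power is 96.5%, in line with the stated figure of about 95%. The point at issue does not touch this number.

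**2. Where Day 253 falls** (SAP 4 dosing table; Protocol Table 7, footnote 1):

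| Cohort | Last dose before Day 253 | Days since dose / interval |
|---|---|---|
| 1 | Day 225 | 28/28 |
| 2 | Day 211 | 42/42 |
| 3 | Day 197 | 56/56 |
| 4 | Day 197 | 56/84 |

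The mismatch is real.

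**3. Its size in exposure.** Assume one compartment, equal volumes and a half-life h of 43 days (39 to 48, Protocol 6.2). Retained dose = Σ dose × 2^(-(t - t_dose)/h). At h = 43:

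- Day 253, Cohorts 1/2/3/4: 1751/1670/1655/2952 mg. Cohort 4 is 1.69 to 1.78 times the others (1.66 to 1.81 over the half-life range).
- Cohort 4 at Day 281: 1880 mg, which is 1.07 to 1.14 times the others' Day 253 values (1.01 to 1.18).
- Day 197, a trough shared by Cohorts 1, 3 and 4: 1749/1681/1882 mg, a ratio of 1.08 to 1.12 (1.01 to 1.15).

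The documents give no figure for what this does to LDH. If Cohort 4's change were 10 points worse at Day 281 than at Day 253 (assumed; range 5 to 20), a trough-matched pooled mean would differ by 10 × 6/24 = 2.5 to 10 × 8/26 = 3.1 points (1.3 to 6.2), against a planned effect of 40.

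**4. What a Day 281 level would do to the covariance.** The postbaseline LDH visits are Days 7, 15, 22, 29, 43, 57, 85, 113, 127, 141, 169, 197, 211, 225 and 253. That is 15 visits, hence 15 × 16/2 = 120 covariance parameters. A sixteenth gives 16 × 17/2 = 136.

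- Day 253 given an intercept and 14 earlier visits has 15 coefficients. With 20 to 26 patients, 5 to 11 residual df remain, so the covariance is estimable.
- Day 281 given an intercept and 15 earlier visits has 16 coefficients for 6 to 8 patients. The residual is zero, and the log-likelihood rises by n × ln 10 = 13.8 (n = 6) to 18.4 (n = 8) per tenfold fall in residual SD, without limit.
- FACIT-Fatigue has 7 postbaseline visits (Protocol Table 7), so 8 coefficients for 6 to 8 patients, with the same result.

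**5. What would follow for Day 253.** With Day 281 entered, each of the three fallback structures converged in 20 of 20 simulated trials, so a move to Wilcoxon is not shown. In standard form these structures assume one variance for all visits. The approximate ratio of the reported to the correct Day 253 standard error, with f the assumed SD inflation at the unusual visits, is:

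- All SDs equal: 1.00.
- Two of the other visits inflated: √((2f² + 13)/15) = 1.08 (f = 1.5) and 1.18 (f = 2).
- Day 253 alone inflated: √((14 + f²)/15)/f = 0.69 and 0.55.

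At the planning values t = 40/(45/√20) = 3.98. With the standard error 18% too large it is 3.98/1.18 = 3.4, against 2.09 on 19 df. Where the error is understated, the correctly scaled t of 3.98 still rejects; the cost is an interval that is too narrow.

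**6. How the text resolves.** SAP 7.2.1 ties the model to the combined cohorts, a phrase absent from Protocol 16.6, and in this report Day 281 belongs to one cohort. Endpoint and test are fixed at Day 253. The last-observation rule fills a missing Day 253, and a later value cannot be carried back to it, so Day 281 needs no role there.

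**The case for a change.** The best case for a change is that the phrase about combined cohorts may describe pooling rather than a choice of visits. Two programmers could then follow the SAP and fit different models, and one fit would be degenerate. A primary model should not hang on that, and one sentence would settle it. Likewise, having added Day 281 to show efficacy at trough, the plan could pair it with the other cohorts' troughs at little cost.

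What stands is that the visit list is missing and that no LDH or hemolysis-marker table is indexed to the end of the dosing interval. The rest does not carry. A level seen only in Cohort 4 is not a natural combined-cohort time point, and anyone who tried it would see the unstructured fit fail. The standard-error shifts come from assumed SD patterns and vanish when SDs are equal.

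On the comparison, SAP 7.2.1 and 7.2.2 already summarize LDH and the markers at every visit by cohort. Day 197 gives a same-day trough for three of the four cohorts. SAP 7.2.4.1 plans serum trough after each cohort's last maintenance dose, and the transfusion window in SAP 7.2.3 ends at Day 253 or Day 281 as appropriate. A paired table would mostly rearrange printed numbers. It would also set a ±5-day visit window beside a ±2-day one and mix study days 28 days apart. The footnotes to Protocol Table 11, unlike those to Table 7, do not say that laboratory samples are drawn predose.

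**Conclusion.** No change to the plan is needed. The gap is a missing detail that analysts would most naturally fill by fitting the pooled model through Day 253 and reporting Cohort 4's Day 281 values descriptively. The trough mismatch is genuine: about 1.7 to 1.8 times the other cohorts' retained dose at Day 253, against about 1.1 times at matched trough, under a one-compartment assumption. It bears on descriptive cohort comparisons only, and the figures needed to read them are already planned. Nothing here shows a changed Day 253 conclusion.

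This rests on the SAP's planning values for the test, and on Cohort 4 having no dose between Days 197 and 281, as both documents' dosing tables and the Table 7 footnote say. The Table 7 grid, as extracted, shows an administration mark on Day 253 for Cohort 4. That may be an extraction fault; if it is in the source document, those passages must be reconciled, because Day 281's status as a trough depends on it.
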